## Informed Consent

12) Capable of giving signed informed consent (Section 10.1.3), which includes compliance with the requirements and restrictions listed in the ICF and in this protocol, and willing to participate in the study.

## 5.2 Exclusion Criteria

Subjects are excluded from the study if any of the following criteria apply:

### Medical Conditions

- 1) Known active hepatitis B (eg, HBsAg reactive), or hepatitis C (eg, HCV RNA [qualitative] is detected), or chronic hepatitis B or C infection or human immunodeficiency virus (HIV) infection in medical history, with the following exceptions:
  - a) Those with a history of hepatitis with a negative polymerase chain reaction (either qualitative or quantitative) OR have documentation of stable disease with aspartate aminotransferase (AST)/serum glutamic oxaloacetic transaminase and alanine aminotransferase (ALT)/serum glutamic pyruvic transaminase  $<2.0 \times$  upper limit of normal (ULN) may be eligible for this study.
  - b) Subjects with history of HIV who have an undetectable viral load for the prior 3 months, and who agree to maintain antiviral therapy, may be eligible for the study.
- 2) Significant medical diseases or conditions, as assessed by the investigators and sponsor, that would substantially increase the risk benefit ratio of participating in the study. This includes, but is not limited to, acute myocardial infarction within the last 6 months, unstable angina, uncontrolled diabetes mellitus, significant active infections, and congestive heart failure New York Heart Association Class III-IV.
- 3) Abnormal biochemical indices as listed below:
  - a) Aspartate aminotransferase/serum glutamic oxaloacetic transaminase and ALT/serum glutamic pyruvic transaminase  $>3.0 \times$  ULN.
  - b) Total or direct bilirubin  $>1.5 \times$  ULN or  $>3.0 \times$  ULN and primarily unconjugated unless the participant has a previously documented history of Gilbert's syndrome or genetic equivalent.
  - c) Serum creatinine  $>1.5 \times$  ULN, calculated glomerular filtration rate (GFR)  $<40$  mL/min/1.73 m^2, or calculated creatinine clearance  $<50$  mL/min by Cockcroft Gault formula or other medically acceptable formulas.
- 4) Known inherited or acquired bleeding disorders that require medication or medical intervention.

- 5) Second malignancy, except treated basal cell or localized squamous skin carcinomas, localized prostate cancer, or other malignancies for which subjects are not on active anticancer therapies and have had no evidence of active malignancy for at least  $\geq 1$  year.

### **Prior/Concomitant Therapy**

- 6) Immediate eligibility for an allogeneic SCT, as determined by the investigator, with an available donor.
- 7) Prior therapy for MDS with chemotherapy, allogenic SCT, or  $\geq 1$  full cycle of treatment with any HMA.
- 8) History of therapy-related MDS, MDS evolving from a pre-existing myeloproliferative neoplasm (MPN), MDS/MPN including CMML, atypical chronic myeloid leukemia, juvenile myelomonocytic leukemia, and unclassifiable MDS/MPN.
- 9) Prior anti-CD47 treatment.
- 10) Previous SCT within 6 months before first dose administration, active graft-versus-host disease, or requiring transplant-related immunosuppression.

### **Other Exclusions**

- 11) Known or suspected hypersensitivity to decitabine, cedazuridine, magrolimab, or any of their excipients.
- 12) Known significant mental illness or other condition such as active alcohol or other substance abuse or addiction that, in the opinion of the investigator, predisposes the subject to high-risk of noncompliance with the protocol.
- 13) Clinical suspicion of active central nervous system (CNS) involvement by MDS.
- 14) History of psychiatric illness or substance abuse likely to interfere with the ability to comply with protocol requirements or give informed consent.
- 15) Pregnant or actively breastfeeding.

### **5.3 Lifestyle Considerations**

Subjects are required to adhere to all guidelines in this section.

#### **5.3.1 Meals and Dietary Restrictions**

Oral decitabine/cedazuridine tablets should be taken with water on empty stomach (defined as having no food for 2 hours before dosing) with no food for 2 hours after administration (Section 4.5).

### 5.3.2 Contraceptive Requirements

Lifestyle considerations pertaining to contraceptive requirements while on study are described in Section 10.2 for both men and women. Magrolimab has a longer half-life than oral decitabine/cedazuridine, which forms the basis of the duration of contraceptive requirements for both men and women.

### 5.3.3 Type and Screen and Direct Antiglobulin Test

Magrolimab may interfere with RBC phenotyping due to expected coating of the RBC membrane. Due to the risk of developing anemia, and because magrolimab may make phenotyping difficult, any of the 4 blood groups (A, B, AB, and O)/Rhesus factor (ABO/Rh) type, antibody screen, extended phenotyping or genotyping, and DAT need to be performed at screening before exposure to magrolimab, as described in Section 8.5.7.

Red blood cell genotyping (instead of an extended RBC phenotyping) must be performed if a subject received any RBC or whole blood transfusion within the previous 3 months (unless the laboratory has availability for special techniques for performing phenotyping for subjects with a recent transfusion). Extended RBC genotyping instead of extended RBC phenotyping is acceptable for any subject. Red blood cell phenotyping/genotyping, ABO type, and DAT need not be repeated if results dated before screening are available. Antibody screen need not be repeated if results dated before screening are available, unless the subject was transfused since that time. Results must be available before the first dose of magrolimab.

## 5.4 Screen Failures

Screen failures are defined as subjects who consent to participate in the clinical study (ie, sign the ICF), but are not subsequently treated. A minimal set of screen failure information is required to ensure transparent reporting of screen failure subjects to meet the Consolidated Standards of Reporting Trials publishing requirements and to respond to queries from regulatory authorities. Minimal information includes demography, screen failure details, eligibility criteria, and any screening procedure-related AEs.

Individuals who do not meet the criteria for participation (screen failure) may be rescreened (no minimum time is required before rescreening and the number of times a subject can be rescreened is limited to 2). Rescreened subjects should be assigned the same subject number as for the initial screening.

## 6.0 STUDY INTERVENTIONS AND CONCOMITANT THERAPY

### 6.1 Description of Study Interventions Administered

Descriptions of the study treatments to be administered are shown in [Table 8](#). ASTX727 and oral decitabine/cedazuridine are often used interchangeably.

**Table 8: Oral Decitabine/Cedazuridine and Magrolimab Products Used in the Study**

	Single Arm	
	Oral Decitabine/Cedazuridine (also known as ASTX727) a,b	Magrolimab
Intervention Name	Oral decitabine/cedazuridine	Magrolimab
Type	Drug	Drug
Dose Formulation	Tablet	IV
Unit Dose Strength(s)	35 mg decitabine and 100 mg cedazuridine	1 mg/kg, 15 mg/kg, and 30 mg/kg
Dosage Level(s)	
Cycle 1:
 
 
One tablet QD on Days 1-5a
 
 
Cycles <math>\geq</math>2:
 
 
One tablet QD on Days 1-5a
 
	
Priming Dose:
 
 
1 mg/kg on Days 1 and 4
 
15 mg/kg on Day 8
 
30 mg/kg on Days 11, 15, followed by weekly administration for 5 doses (on Day 22, Day 29, Day 36, Day 43, and Day 50)
 
 
Maintenance Dose:
 
 
30 mg/kg on Day 57 and
 
30 mg/kg every 14 days thereafter
 

Route of Administration	PO	IV
Sourcing	Provided centrally by the sponsor	Provided centrally by the sponsor
Packaging and Labeling	Provided in 5-count opaque high-density polyethylene bottle with child resistant closure. Each bottle labeled per country requirement.	Single-use, 10 mL vials containing 200 mg of the antibody in a formulation of 10 mM sodium acetate, 5% (w/v) sorbitol, 0.01% (w/v) polysorbate 20, at a pH of 5.0.

DLT=dose-limiting toxicity; IV=intravenous; PO=by mouth; QD=once daily; w/v=weight by volume

a. ASTX727 and oral decitabine/cedazuridine are often used interchangeably.

b. Dosing may be modified if DLTs are observed in the DLT cohort.

### 6.2 Preparation/Handling/Storage/Accountability

The investigator or designee must confirm appropriate temperature conditions have been maintained at the study center for all study intervention received and any discrepancies are reported and resolved before use of the study intervention.

Only subjects enrolled in the study may receive study intervention and only authorized site staff may supply or administer study intervention. All study intervention must be stored in a secure, environmentally controlled, and monitored (manual or automated) area in accordance with the labeled storage conditions with access limited to the investigator and authorized site staff.

Store oral decitabine/cedazuridine tablets at room temperature at 20°C to 25°C (68°F to 77°F); excursions from 15°C to 30°C (59°F to 86°F) are permitted. Excursions for  $\leq$ 7 days at temperatures  $>30^\circ\text{C}$  (86°F) and  $\leq 40^\circ\text{C}$  (104°F) are not expected to affect the strength or stability; however, excursions at these temperatures for  $>7$  days may impact investigational medicinal product (IMP) quality depending upon severity. Excursion at temperatures  $<15^\circ\text{C}$  (59°F) or  $>40^\circ\text{C}$  (104°F) for any amount of time will impact IMP quality. For those temperature excursions that impact IMP quality, the IMP should be quarantined and stored at the recommended temperature, while the Astex staff is contacted for further instructions.

Instructions regarding transport from pharmacy to home and at-home storage instructions should be given to the study subject, as applicable.

Magrolimab is supplied in single-use, 10 mL vials containing 200 mg of the antibody in a formulation of 10 mM sodium acetate, 5% (weight by volume) sorbitol, 0.01% (weight by volume) polysorbate 20, at a pH of 5.0.

The labeling complies with the requirements of the applicable regulatory agencies. Vials containing magrolimab should be stored under refrigeration at 2°C to 8°C (36°F to 46°F) in an appropriate, locked room and/or locked refrigerator, accessible only to pharmacy personnel or a duly designated person. Magrolimab should not be frozen. Protect from light during storage. **DO NOT SHAKE.**

Additional details about oral decitabine/cedazuridine and magrolimab are provided in the Pharmacy Manual.

The investigator, institution, or the head of the medical institution (where applicable) is responsible for study intervention accountability, reconciliation, and record maintenance (ie, receipt, reconciliation, and final disposition records).

Further guidance and information for the final disposition of unused study interventions are provided in the Pharmacy Manual.

### **6.3 Measures to Minimize Bias: Randomization and Blinding**

This study is not blinded or randomized; therefore, bias may occur. To minimize bias, response assessments to determine efficacy will be assessed by the investigator and calculated using a pre-specified program based on the 2006 IWG criteria (Section 10.6) and methods to assess CR as described in 2006 ([Cheson et al 2006](#)), as defined in [Table 21](#) and [Table 22](#).

## 6.4 Study Intervention Compliance

Subject compliance with oral decitabine/cedazuridine will be assessed at time points defined in the SoA ([Table 1](#)). Compliance will be assessed by direct questioning, counting returned tablets, and reviewing subject's dosing diaries. Deviation(s) from the prescribed dosage regimen should be recorded in the subject's dosing diary.

Treatment start and stop dates, including dates and reasons for treatment interruption and/or dose modifications will also be recorded in the electronic case report form (eCRF).

## 6.5 Premedication

Premedication is required prior to the administration of magrolimab through the Day 22 infusion of priming and repriming. Premedications may be continued based on the treating physician's clinical judgment and the presence/severity of prior infusion-related reactions. In the case of a Grade 3 infusion-related reaction, a premedication regimen for subsequent infusions is required ([Section 8.5.7.2](#)).

Premedications are oral acetaminophen 650 mg to 1000 mg and oral or IV diphenhydramine 25 mg to 50 mg or comparable regimen. If less than 4 hours have elapsed since a prior dose of acetaminophen has been given, the dose of acetaminophen premedication may be omitted.

These premedications are to be entered as concomitant medications.

## 6.6 Dose Modification

### 6.6.1 Oral Decitabine/Cedazuridine Dose Modifications

In the event of toxicity that prevents initiation of a subsequent cycle containing oral decitabine/cedazuridine, the first intervention is dosing delay rather than dosing reduction. Subsequent cycles should be delayed in subjects with an absolute neutrophil count  $\leq 500$  cells/ $\mu$ L, until recovery to  $>500$  cells/ $\mu$ L. Delays of up to 2 weeks are acceptable without a change in dosing. The planned dosing of oral decitabine/cedazuridine may be reduced for individual subjects in the event of unacceptable treatment-related toxicity or delay in initiating a treatment cycle (eg, an AE that meets the definition of a DLT) as assessed by the investigator ([Section 8.5.6](#)), and should be reduced based on the guidelines outlined in [Table 9](#).

When delays are required, the following parameters should be followed:

- If dosing of oral decitabine/cedazuridine is delayed more than 3 days prior to Day 15, then the next dosing of oral decitabine/cedazuridine will be further delayed to align with the next dose of magrolimab.
- If oral decitabine/cedazuridine is delayed to Day 15 of a cycle, then that cycle length will be increased to 42 days. The next cycle will start 28 days after Day 15.

- If oral decitabine/cedazuridine is delayed beyond 15 days into a cycle, then administration of oral decitabine/cedazuridine will be held for that cycle.

**Table 9: Dosing Reduction Guidelines for Oral Decitabine/Cedazuridine**

Number of Dose Reductions per Individual Subject	Dose per Cycle
Level 1	Oral decitabine/cedazuridine Daily×5 for each 28-day cycle
Level 2	Oral decitabine/cedazuridine Daily×4 for each 28-day cycle
Level 3	Oral decitabine/cedazuridine Daily×3 for each 28-day cycle
Level 4	Oral decitabine/cedazuridine on Days 1, 3, and 5 of each 28-day cycle
Level 5	Discontinue oral decitabine/cedazuridine

DLT=dose-limiting toxicity

Note: For subjects receiving oral decitabine/cedazuridine outside of the period of DLT assessment in the DLT cohort, a maximum of 2 dose reductions are allowed before study treatment must be permanently discontinued.

## 6.6.2 Magrolimab Dose Modifications

In clinical experience with magrolimab, no significant dose-dependent toxicities have been identified. Therefore, in general, dose modifications or delays to magrolimab should not be made. The dose of magrolimab may be reduced for Grade  $\geq 3$  AEs that are deemed clearly related to magrolimab and not oral decitabine/cedazuridine and that do not resolve to Grade  $\leq 2$  or baseline value within 14 days of onset. However, dose delay of magrolimab should occur first, and if the AE does not resolve, then a magrolimab dose reduction can be considered (Section 6.6.2.1). If there is a delay of dosing of magrolimab during a cycle of oral decitabine/cedazuridine, the cycle can be extended by up to 14 days to allow for dosing of the study drug(s) on Day 1 of the subsequent oral decitabine/cedazuridine cycle. The Medical Monitor should be notified of any planned dose delays.

If a magrolimab dose reduction is considered, an initial 33% dose reduction (from 30 to 20 mg/kg) should be done first. If no improvement is observed within at least 28 days, further magrolimab dose reductions from 20 to 15 mg/kg may be warranted. For persistent BM hypocellularity or peripheral cytopenias (where both oral decitabine/cedazuridine and magrolimab may have a contribution), the dose of oral decitabine/cedazuridine should be reduced first. Subjects can re-escalate to higher doses of magrolimab up to the original 30 mg/kg dose if AEs improve, after discussion with the sponsor's Medical Monitor.

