#### 4.5 Dosing Administration

The treatment administration schedule for oral decitabine/cedazuridine and magrolimab is presented in [Table 5](#) and [Table 6](#). The detailed PK assessment schedule is presented in [Table 13](#) and [Table 14](#).

The following magrolimab dosing regimen is proposed for this study:

- The dose of magrolimab is increased over time in a series called priming doses. Priming doses of magrolimab: 1 mg/kg on Days 1 and 4; 15 mg/kg on Day 8; 30 mg/kg on Days 11, 15, 22, 29, 36, 43, and 50.
- Maintenance doses of magrolimab: 30 mg/kg on Day 57 and every 14 days thereafter.
- If magrolimab is not administered for 28 days or more and then restarted, the resulting doses, called repriming doses, follow the same schedule and dose level as the first 22 days of the priming doses, then maintenance dosing can start 7 days later. For subjects who have not received at least one 30 mg/kg dose of magrolimab (ie, for subjects who have either not received their first dose of 30 mg/kg or subjects who have received doses <30 mg/kg), a dose delay of only 14 days is allowed until repriming is required.

The duration of each magrolimab infusion including flush will be 3 hours ( $\pm 30$  minutes) for the first 3 doses of priming and repriming. Recommended premedications are listed in [Section 6.5](#). After the third dose of treatment, the magrolimab infusion including flush will be 2 hours ( $\pm 30$  minutes). The reduced infusion time to 2 hours is based on prior data demonstrating the majority CD47 receptor occupancy (RO) on peripheral blood cells, thus mitigating anticipated RBC toxicities from magrolimab.

Oral decitabine/cedazuridine study treatment is to be administered according to the following schedule:

- Days 1-5: oral decitabine/cedazuridine by mouth daily on an empty stomach (morning before breakfast) with no food for 2 hours before and at least 2 hours after administration. When taking oral decitabine/cedazuridine, subjects may have clear liquids such as water, black coffee, or tea. The dosing regimen may be modified during assessment of DLTs in the DLT cohort ([Section 4.1.1](#)).

**Table 5:** Treatment Administration Schedule for Oral Decitabine/Cedazuridine

Day →	1	2	3	4	5	6-28
All Cycles	×	×	×	×	×	—

DLT=dose-limiting toxicity; FDC=fixed-dose combination; "×"=dosing day; "—"=non-dosing day

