### 6.6.2.1 Repriming for Magrolimab

Given the large CD47 antigen sink on normal cells, subjects who have a dose delay of magrolimab equivalent to 28 days or more are required to be reprimed with magrolimab to resaturate the CD47 antigen sink. Within 24 hours prior to each of the repriming doses of magrolimab, all subjects must have a documented Hgb  $\geq 9$  g/dL. Subjects who do not meet these criteria must be transfused and

have their Hgb rechecked to meet the minimum Hgb threshold prior to each of the first 2 doses of magrolimab. During the first 2 doses of repriming, blood testing of Hgb will be required 3 to 6 hours after a magrolimab dose and the results must be reviewed prior to discharging the subject from clinic. The subject should be transfused as clinically appropriate.

Repriming differs depending on where the participant is in their treatment period as follows:

- 1) For subjects who have not reached Day 57 of magrolimab, up to 14 days between doses is permitted.
- 2) For subjects who have received Day 57 (or beyond) dose of magrolimab, up to 28 days between doses is permitted.

After Day 22 of repriming, subjects should return to their original maintenance dose schedule.

Please notify the Medical Monitor of any planned dose delays.

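### The magrolimab repriming schedule makes no exception for a dose-reduced subject, so it can return that subject to 30 mg/kg without the conditions Section 6.6.2 sets for re-escalation

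*Combined protocol and SAP*

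**What the plan says.** Section 6.6.2 covers reductions of magrolimab for Grade 3 or higher events clearly attributed to it that are still above Grade 2 and above baseline 14 days after they began. Delay comes before reduction: "dose delay of magrolimab should occur first, and if the AE does not resolve, then a magrolimab dose reduction can be considered". The first step is fixed: "If a magrolimab dose reduction is considered, an initial 33% dose reduction (from 30 to 20 mg/kg) should be done first". If there is no improvement, "further magrolimab dose reductions from 20 to 15 mg/kg may be warranted". The way back up is conditional: "Subjects can re-escalate to higher doses of magrolimab up to the original 30 mg/kg dose if AEs improve, after discussion with the sponsor's Medical Monitor".

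The repriming rule appears in Sections 1.1 and 4.5, Table 2 note b, Table 4 note d and the note to Table 6. After a gap of 28 days or more, the repriming doses "follow the same schedule and dose level as the first 22 days of the priming doses". Table 4 note d gives the figures: 1 mg/kg on Days 1 and 4, 15 mg/kg on Day 8, and 30 mg/kg on Days 11, 15 and 22. Section 6.6.2.1 makes repriming obligatory and ends: "After Day 22 of repriming, subjects should return to their original maintenance dose schedule". Section 4.5 defines maintenance as 30 mg/kg every 14 days from Day 57.

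No section gives a repriming schedule, or an exception, for a subject already lowered to 20 or 15 mg/kg.

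**The concern.** A reduction under Section 6.6.2 follows a severe event attributed to magrolimab, and two safeguards stand between the reduced dose and 30 mg/kg: improvement of the event and a discussion with the Medical Monitor. The repriming rule leads to 30 mg/kg by day count alone. If a reduced subject meets the repriming trigger while either safeguard is unmet, a site that follows the repriming schedule departs from Section 6.6.2, and a site that holds the reduced dose departs from the repriming schedule.

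Safety of the individual subject is the first stake. The second is interpretability. Adverse events are part of the primary endpoint (Section 3.0) and about 58 sites are planned (Section 4.4), so the same event could be followed by different exposure at different sites, each able to cite the protocol.

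**Working it through.** No sample-size or error-rate calculation applies. The check compares the dosing rules, with a little arithmetic for scale.

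**1. The plan's own figure.** Section 6.6.2 calls 30 to 20 mg/kg a 33% reduction. 1 − 20/30 = 0.333, so the figure reproduces. The second step is 1 − 15/20 = 0.25, and both steps together are 1 − 15/30 = 0.50.

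**2. Repriming doses against the reduced levels.** Doses are from Table 4 note d and reduced levels from Section 6.6.2. Ratio = repriming dose ÷ reduced level.

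| Repriming day | Dose (mg/kg) | Ratio to 20 | Ratio to 15 |
|---|---|---|---|
| 1 | 1 | 0.05 | 0.07 |
| 4 | 1 | 0.05 | 0.07 |
| 8 | 15 | 0.75 | 1.0 |
| 11 | 30 | 1.5 | 2.0 |
| 15 | 30 | 1.5 | 2.0 |
| 22 | 30 | 1.5 | 2.0 |

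The first three doses are at or below either reduced level. The last three of the six exceed both.

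**3. Conditions for reaching 30 mg/kg.**
- Section 6.6.2: the event has improved, and re-escalation has been discussed with the Medical Monitor.
- Repriming rule: the calendar day only.

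If both conditions of Section 6.6.2 are met, the rules agree. If either is unmet, they give different doses on Days 11, 15 and 22.

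**4. Does other text settle it?**
- The sentence in Section 6.6.2 that puts delay before reduction refers the reader to Section 6.6.2.1, which is silent on the dose level for a reduced subject.
- Sections 1.1 and 4.5 point to Section 6.6.2 for reductions in general, but do not say which rule governs repriming.
- Sections 6.6.2 and 6.6.2.1 require the Medical Monitor to be told of planned delays. Being told of a delay is not a discussion of re-escalation.
- Section 6.8 defines overdose against the assigned dose in Section 6.1, and Table 8 there lists only 1, 15 and 30 mg/kg. It does not clearly flag 30 mg/kg in a reduced subject.

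**5. Can the case arise?** By two routes. A subject already reduced may later have a gap long enough to trigger repriming. Or a subject on hold, to be restarted at a reduced dose, may be held long enough to trigger it. The conflict does not depend on which trigger applies once it is met.

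**6. Maintenance afterwards.** The closing sentence of Section 6.6.2.1 can mean the 14-day interval or the 30 mg/kg dose. The text does not decide between them. Days 11 to 22 of repriming carry no such ambiguity.

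**The case against.** The best counter-argument is that the repriming schedule is a default. Sections 1.1 and 4.5 state it alongside a pointer to Section 6.6.2, and Table 6 fixes maintenance at 30 mg/kg without exception although nobody would read that as forbidding reductions. On this view the protocol merely lacks a clarification. The plan also says that magrolimab should in general not be modified and calls reductions rare. The study is single-arm with descriptive safety summaries.

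The points on frequency and statistical impact stand. The default argument only partly stands. Repriming is not just the background schedule: it is a mandatory course with an expressly stated dose level, triggered by the kind of delay that Section 6.6.2 requires before a reduction. A general pointer does not say that Section 6.6.2 overrides it.

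A reader might go further and infer that every reduction before Day 57 forces repriming, because the event must be unresolved at 14 days and Section 6.6.2.1 says "For subjects who have not reached Day 57 of magrolimab, up to 14 days between doses is permitted". The documents do not support that, for two reasons.
- The 14 days in Section 6.6.2 run from onset of the event and are not a dosing hold; the required delay has no minimum length. As an illustration of what the text permits: onset on Day 24, the Day 29 dose given, the Day 36 dose held. Fourteen days from onset is Day 38. A reduced dose on Day 39 comes 39 − 29 = 10 days after the last infusion, inside the 14-day limit.
- Sections 1.1 and 4.5, Table 2 note b, Table 4 note d and Table 6 apply the 14-day limit to subjects who have not yet had a 30 mg/kg dose, and otherwise use 28 days. The opening of Section 6.6.2.1 also uses 28 days.

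**Conclusion.** The conflict is in the text, but it is conditional. It arises for a subject who has been reduced, or is to be reduced after a delay, who then meets the repriming trigger, and for whom the event has not improved or re-escalation has not been discussed. In that case three of six infusions are 1.5 or 2.0 times the reduced level. Where both conditions of Section 6.6.2 are met there is no contradiction.

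This rests on reading the repriming dose level literally, as Table 4 note d spells it out. It assumes nothing about how often the case occurs. The documents give no frequency, and their own wording suggests few subjects.

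Two further inferences should not be drawn. That every reprimed subject stays at 30 mg/kg in maintenance is not established, since the closing sentence of Section 6.6.2.1 may concern the interval only. And a percentage excess in total drug over the repriming course would need a reduced-dose repriming schedule as comparator, which the documents do not contain; the per-infusion ratios are as far as the text goes.

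The point is worth correcting because, followed literally, a stated rule bypasses stated safety conditions. It does not bear on sample size, power or type I error.

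**What to change.** Reconcile Section 6.6.2 with Sections 6.6.2.1, 1.1 and 4.5, Table 2 note b, Table 4 note d and Table 6. One passage should state which rule governs the dose level during repriming, and at the maintenance doses that follow, for a subject on or moving to a reduced magrolimab dose; the other places should refer to it. Reword the end of Section 6.6.2.1 so that it is clear whether dose, interval or both are meant. Which rule applies is for the sponsor's clinical team to decide, and this review takes no position on it.

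The cost is one clarifying sentence in an amendment and matching table notes. No extra subjects, visits or data are needed.
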